5 ELIGIBILITY CRITERIA

5.1 Inclusion criteria

Patient volunteers who meet all of the following criteria are eligible for this trial:

1. Is male or female aged 18 years or over.
2. Has documented HIV-1 infection.
3. Is capable of giving informed consent.
4. Is willing to comply with the protocol requirements.
5. Virologically suppressed (plasma HIV-RNA <50 copies/mL) and on a stable regimen for >24 weeks.
6. Subjects are required to have a history of the K103N mutation (acquired or selected). Subjects who at any time have had the mutations 100I, 101E/P, 106A/M, 138K/G/Q, 181C/I/V, 188L, 190A/S/E/Q, 230L mutations are to be excluded. Other NNRTI region variants can be included. All PI and NRTI mutations are acceptable. Study sites may ask the coordinating centre for advice as required.
7. Subjects must have never failed INSTI (2 x VL >200 >2 weeks apart) but current regimen can include INSTI.
8. A female, may be eligible to enter and participate in the study if she:

is of non-child-bearing potential defined as post-menopausal (12 months of spontaneous amenorrhea without an alternative medical cause and \geq 45 years of age). A high follicle stimulating hormone (FSH) level consistent with postmenopausal status may be used to confirm a post-menopausal state in women who are not using hormonal contraception) or hormonal replacement therapy at the discretion of the PI. However, in the absence of 12 months of amenorrhea, a single FSH measurement alone is insufficient.

OR is physically incapable of becoming pregnant with documented tubal ligation, hysterectomy or bilateral oophorectomy or,

OR is of child-bearing potential with a negative pregnancy test at Screening (& baseline visit) and agrees to use one of the following methods of contraception to avoid pregnancy:

- True abstinence from penile-vaginal intercourse from 2 weeks prior to administration of IP, throughout the study, and for at least 2 weeks after discontinuation of all study medications (When this is in line with the preferred and usual lifestyle of the subject.) (Periodic abstinence (e.g., calendar, ovulation, symptothermal, post-ovulation methods), and

CONFIDENTIAL

- withdrawal are not acceptable methods of contraception];
- Any intrauterine device (IUD) with published data showing that the expected failure rate is <1% per year (not all IUDs meet this criterion, see Appendix 3 for an example listing of approved IUDs);
 - Male partner sterilisation confirmed prior to the female subject's entry into the study, and this male is the sole partner for that subject;
 - Approved hormonal contraception (see appendix 4 for a listing of examples of approved hormonal contraception);
 - Any other method with published data showing that the expected failure rate is <1% per year;
 - Any contraceptive method must be used consistently and for at least 2 weeks after discontinuation of IP.
9. If a heterosexually active male, he is using effective birth control methods and is willing to continue practising these birth control methods during the trial and until follow-up visit.
10. Subjects currently receiving DTG or RPV, but not both, can be included.

5.2 Exclusion criteria

Patients meeting 1 or more of the following criteria cannot be selected:

1. Infected with HIV-2.
2. Detectable HIV-1 RNA at screening (HIV-1 RNA measurement ≥ 50 c/mL).
3. Subjects requiring regular dosing doing with H2 or PPI antacid medications or a history of achlorhidria or drug known to interact with RPV or DTG.
4. Use of medications that are associated with Torsades de Pointes.
5. Corrected QT interval (QTc [Bazett]) >450 milliseconds or QTc (Bazett) >480 milliseconds for participants with bundle branch block. The QTc is the QT interval corrected for heart rate according to Bazett's formula (QTcB).
6. Unstable health conditions (i.e. opportunistic infections, cancers, unstable liver disease etc).
7. Any evidence of an active Centres for Disease Control and Prevention Category C disease. Exceptions include cutaneous Kaposi's sarcoma not requiring systemic therapy and historic CD4+ lymphocyte counts of <200 cells/millimeter³.

CONFIDENTIAL

8. History or presence of allergy to the study drugs or their components or drugs of their class.
9. Ongoing malignancy other than cutaneous Kaposi's sarcoma, basal cell carcinoma, or resected, non-invasive cutaneous squamous cell carcinoma, or cervical intraepithelial neoplasia; other localised malignancies require agreement between the investigator and the Study medical monitor for inclusion of the subject prior to randomisation.
10. Any pre-existing physical or mental condition which, in the opinion of the Investigator, may interfere with the subject's ability to comply with the dosing schedule and/or protocol evaluations or which may compromise the safety of the participants. Subjects considered to pose a significant risk of suicide should be excluded.
11. Any condition which, in the opinion of the Investigator, may interfere with the absorption, distribution, metabolism or excretion of the study drugs or render the subject unable to take oral medication.
12. Using any concomitant therapy disallowed as per the reference safety information and product labelling for the study drugs. Specifically, co-administration with the following medicinal products is not allowed:
 - dofetilide or pilsicainide;
 - fampridine (also known as dalfampridine);
 - carbamazepine, oxcarbazepine, phenobarbital, phenytoin;
 - rifampicin, rifapentine;
 - proton pump inhibitors, such as omeprazole, esomeprazole, lansoprazole, pantoprazole, rabeprazole;
 - systemic dexamethasone, except as a single dose treatment;
 - St John's wort (*Hypericum perforatum*).
13. Has acute viral hepatitis including, but not limited to, A, B, or C.
14. Active hepatitis B/ Hep B non-immune subjects who have failed vaccination (antibody concentration < 10 international units). (If local practice does not include vaccination of low risk patients, then the patients without HBsAb are not excluded – this must be clearly documented in the medical records and eCRF). Note: subjects can be re screened if they receive vaccination and subsequently meet eligibility criteria.
15. Evidence of Hepatitis B virus (HBV) infection based on the results of testing at Screening for Hepatitis B surface antigen (HBsAg), Hepatitis B core antibody (anti-HBc), and Hepatitis B surface antibody (HBsAb)

CONFIDENTIAL

as follows: Participants positive for HBsAg are excluded; Participants positive for anti-HBc (negative HBsAg status) and negative for HBsAb are excluded (if local practice does not include vaccination of low risk patients, then the patients without HBsAb are not excluded – this must be clearly documented in the medical records and eCRF). Note: Subject positive for anti-HBc (negative HBsAg status) and positive for HBsAb are immune to HBV and are not excluded.

16. Participants with an anticipated need for any Hepatitis C virus (HCV) therapy during the Early Switch Phase and for interferon-based therapy for HCV throughout the entire study period.
17. Any investigational drug within 30 days prior to the trial drug administration.
18. Any evidence of viral resistance different to the one described in the inclusion criteria i.e. not meeting inclusion criteria or having different mutation at K103.
19. Dialysis or renal insufficiency (creatinine clearance < 50ml/min).
20. History of decompensated liver disease (Alanine aminotransferase (ALT) \geq 5 times the upper limit of normal (ULN), OR ALT \geq 3xULN and bilirubin \geq 1.5xULN (with >35% direct bilirubin).
21. Unstable liver disease (as defined by the presence of ascites, encephalopathy, coagulopathy, hypoalbuminemia, esophageal or gastric varices, or persistent jaundice), cirrhosis, known biliary abnormalities (with the exception of Gilbert's syndrome or asymptomatic gallstones).
22. Subjects with severe hepatic impairment (Class C) as determined by Child-Pugh classification (see appendix 4).
23. Opportunistic infection within 4 weeks prior to first dose of DTG plus RPV.
24. Clinical decision that a switch of antiretroviral therapy should be immediate.
25. Screening blood result with any grade 3/4 toxicity according to Division of AIDS (DAIDS) grading scale, except: asymptomatic grade 3 glucose, amylase or lipid elevation, asymptomatic grade 4 triglyceride elevation (re-test allowed) or unconjugated hyperbilirubinaemia due to atazanavir exposure.
26. Any condition (including illicit drug use or alcohol abuse) or laboratory results which, in the investigator's opinion, interfere with assessments or completion of the trial.
27. Women planning pregnancy or who are pregnant or breast feeding. (NB: See section 6.12 Withdrawal Criteria for guidance if pregnancy does occur).
28. Females of childbearing potential and males must be willing to use a highly effective (acceptable effective contraceptive measures are only acceptable for IMP's with unlikely human teratogenicity /

CONFIDENTIAL

fetotoxicity in early pregnancy) method of contraception (hormonal method of birth control; true abstinence). Contraceptive methods that can achieve a failure rate of less than 1% per year when used consistently and correctly are considered as highly effective birth control methods (see Appendix 4).

Such methods include:

- combined (estrogen and progestogen containing) hormonal contraception associated with inhibition of ovulation:
 - oral
 - intravaginal
 - transdermal
- progesteron-only hormonal contraception associated with inhibition of ovulation
 - oral
 - injectable
 - implantable
- Intrauterine device (IUD)
- Intrauterine hormone-releasing system (IUS)
- bilateral tubal occlusion
- vasectomised partner
- true sexual abstinence

(NB: See section 6.12 Withdrawal Criteria for guidance if pregnancy does occur).

29. Hypersensitivity to the active substances or to any of the excipients listed below:

List of excipients

Tablet core

- Mannitol (E421)
- Magnesium stearate
- Microcrystalline cellulose
- Povidone (K29/32)
- Sodium starch glycolate
- Sodium stearyl fumarate
- Lactose monohydrate
- Croscarmellose sodium
- Povidone (K30)
- Polysorbate 20
- Silicified microcrystalline cellulose

Tablet coating

- Polyvinyl alcohol- part hydrolysed
- Titanium dioxide (E171)
- Macrogol
- Talc
- Iron oxide yellow (E172)
- Iron oxide red (E172)

CONFIDENTIAL

6 TRIAL PROCEDURES

The schedule of assessments is summarised in the study flow chart in Appendix 1. From the Baseline visit through to follow up, visits may take place +/- 7 days from that specified at the discretion of the Investigator.

Please note that if additional tests / procedures are required in accordance with local practice then these should still be performed (no usual tests / procedures should be withheld from the patients during the study).

6.1 Recruitment

Following full written informed consent, sites must keep a record of all screening and enrolled participants using screening and enrolment logs. Diagnostic tests/procedures may be used in determining eligibility however, written informed consent must be obtained prior to any study specific procedures. All information collected for eligible participants will be completely anonymised and recorded in the Investigator Site File (ISF).

6.2 Study Registration

All eligible consented participants will be given a unique study identifier via an electronic study database.

Anonymised information that will be collected are:

- age,
- gender,
- ethnicity
- whether the patient is enrolled or not enrolled,
- the reason not eligible for trial participation, or if they are eligible but declined (where available)
Reason for subject wishing to participate

6.3 Patient identification

Patients will be identified through clinic visits by their direct study medical care team and visits will be captured on a participant screening log.

CONFIDENTIAL

6.4 Screening

Written informed consent must be obtained from the subject prior to performing any study related evaluations or procedures.

Subjects will be provided with written information about the study in the form of a Participant Information Sheet (PIS) and will be allowed adequate time for questions and to consider the study before agreeing to participate. It will be the responsibility of the investigator or co-investigator to obtain written informed consent prior to undertaking any procedures detailed in the protocol. This responsibility may be delegated to other suitably trained personnel if allowed according to country-specific regulations and approved by the local ethics committee.

The investigator or designee must provide adequate explanation of the aims, methods, objectives, and potential hazards of the study. It must also be explained to the subject that they are free to refuse or withdraw from the study for any reason without detriment to their future care or treatment.

The following evaluations must be performed within 28 days prior to study randomisation:

- Assessment of subject eligibility according to the inclusion and exclusion criteria
- Demographics
- Medical and social history (past and current), including HIV-associated conditions (see Appendix 1)
- Full antiretroviral history (including resistance history i.e. record all resistance history by major mutations in NRTI, NNRTI, PI and II regions).
- Review of non-antiretroviral medication (any medication taken within the last 30 days)
- Concomitant medication check
- Physical examination including height and weight
- Vital signs (pulse, blood pressure): after 10 minutes resting
- Urinalysis (see Appendix 1) and pregnancy test for WOCBP (β -HCG).
- Laboratory evaluations (non-fasting): haematology and biochemistry (Appendix 1)
- Total cholesterol and lipids (HDL, LDL and triglycerides)
- HIV RNA viral load

CONFIDENTIAL

- HBV antigen test (including HbsAG, anti-HBc and HBsAb , if done as per standard practice) and HCV antibodies test (if test positive for HCV antibodies, test for HCV RNA, if positive and chronic for either HBV or HCV, add AST test to the biochemistry panel at screening visit. Hep B surface antibodies post vaccination levels to be included in assessment, if this is part of local practice)
- ECG
- CD4 & CD8 count / % and ratio

6.5 Consent

The Principal Investigator (PI) retains overall responsibility for the informed consent of participants at their site and must ensure that any person delegated responsibility to participate in the informed consent process is duly authorised, trained and competent to participate according to the ethically approved protocol, principles of Good Clinical Practice (GCP) and Declaration of Helsinki. If delegation of consent is acceptable then details should be provided.

Informed consent must be obtained prior to the participant undergoing procedures that are specifically for the purposes of the trial and are out-side standard routine care at the participating site (including the collection of identifiable participant data unless the trial has prior approval from the Ethics Committee (EC). The right of a participant to refuse participation without giving reasons must be respected.

The participant must remain free to withdraw at any time from the trial without giving reasons and without prejudicing his/her further treatment and must be provided with a contact point where he/she may obtain further information about the trial. Where a participant is required to re-consent or new information is required to be provided to a participant it is the responsibility of the PI to ensure this is done in a timely manner.

The Principal Investigator takes responsibility for ensuring that all vulnerable subjects are protected and participate voluntarily in an environment free from coercion or undue influence.

Where the participant population is likely to include a significant proportion of participants who cannot read or write, require translators or have cognitive impairment, appropriate alternative methods for supporting the informed consent process should be employed. This may include allowing a witness to sign on a

CONFIDENTIAL

participant's behalf (in the case of problems with reading or writing), or allowing someone to date the form on behalf of the participant, or providing PIS in other languages or in a format easily understood by the participant population (in the case of cognitive impairment).

6.6 Randomisation

6.6.1 The randomisation scheme

This study is open label and patients will be randomised to switch at baseline or after 48 weeks. Full details of randomisation scheme will be included in the study randomisation plan.

6.6.2 Method of implementing the allocation sequence

Method will be detailed in the randomisation plan.

6.6.3 Blinding

This section is not applicable.

6.6.4 Unblinding

This section is not applicable.

6.7 Baseline data

The following evaluations and procedures are to be completed pre dose.

- Smoking history
- Alcohol intake
- Recreational drug use
- Symptoms review and adverse events
- Review of concomitant medications
- Physical examination (symptom directed)
- Weight
- Vital signs (pulse, blood pressure: after 10 minutes resting)
- Urinalysis (see Appendix 1)
- Laboratory evaluations: haematology and biochemistry (fasted) (Appendix 1)

CONFIDENTIAL

- Total cholesterol and lipids (HDL, LDL and triglycerides) (fasted)
- HIV RNA viral load as per local laboratory standard method.
Note. In event of viral load failure follow section 6.18 viral failure, resistance assessment & pharmacokinetic assessment procedures.
- Blood sampling for PBMC isolation
(Required unless exemption documented in site contract i.e. if site does not have capacity to process PBMC samples)
- CD4 & CD8 count / % and ratio.
- Quality of life questionnaire (EuroQoL)
- Pittsburgh sleep questionnaire
- Patient treatment satisfaction questionnaire
- DDI assessment
- Drug dispensing
- Adherence assessment
- Pregnancy test for WOCBP (β -HCG).

Note: Investigators to remind females of reproductive potential of the need to avoid pregnancy while in study and adherence to the study's contraception requirements. As a reminder, females of reproductive potential who changed their minds and desire to be pregnant should be withdrawn from the study.

Note: all subjects should be reminded to take precautions to prevent transmission of HIV in accordance with national guidelines.

See Appendix 1 for details of assessments required.

6.8 Study on treatment visits

Study Visits: weeks 4, 12, 24, 48, 52, 72 and 96 (all visits +/- 7 days visit window). An optional visit at week 60 may be performed for subjects on the control arm (3 months after therapeutic modification) as required per national guidelines. The following evaluations and procedures are to be performed pre dose:

- Symptoms review and adverse events
- Review of concomitant medications
- Physical examination (symptom directed)

CONFIDENTIAL

- Weight
- Vital signs (pulse, blood pressure: after 10 minutes resting)
- Viral load
- Alcohol intake, smoking habit and recreational drug use (week 24, 48 and 96)
- Adherence assessment (including date/time of last dose on PK days including ETV visit and/or in the event of virological failure)
- Urinalysis (see Appendix 1) (week 24, 48 and 96)
- Week 48 (and screening) only: HBV antigen test (including HbsAG, anti-HBc and HBsAb, if done as per standard practice) and HCV antibodies test (if test positive for HCV antibodies, test for HCV RNA, if positive and chronic for either HBV or HCV, add AST test to the biochemistry panel at screening visit. Hep B surface antibodies post vaccination levels to be included in assessment, if this is done as per local practice)
- Laboratory evaluations: haematology and biochemistry (fasting)
- Total cholesterol and lipids (HDL, LDL and triglycerides) (fasted)
- PBMC (BL & week 48, 96 & ETV only)
(Required unless exemption documented in site contract i.e. if site does not have capacity to process)
- Pre-dose blood sampling for measurement of DTG & RPV (PK assessment) (week 4 & 48 (experimental arm), week 52 (deferred switch patients) and week 96 (both arms)). Plus pre- or post-dose (as appropriate) at early termination visit and/or in the event of virological failure (see section 6.12). A post dose sample will be taken within 20-28 hours
- HIV RNA viral load
Note. In event of viral load failure follow section 6.18 viral failure & resistance assessment procedures.
- CD4 & CD8 count / % (week 24, 48, 72 and 96)
- EuroQoL questionnaire (week 24, 48 and 96)
- Pittsburgh sleep questionnaire (week 24, 48 and 96)
- Patient treatment satisfaction questionnaire (week 24, 48 and 96)
- DDI assessment (week 24, 48 and 96)
- Adherence assessment
- Drug Dispensing (not at week 96)

CONFIDENTIAL

- Pregnancy test for WOCBP (β -HCG).

Note: Investigators to remind females of reproductive potential of the need to avoid pregnancy while in study and adherence to the study's contraception requirements. As a reminder, females of reproductive potential who changed their minds and desire to be pregnant should be withdrawn from the study.

Note: all subjects should be reminded to take precautions to prevent transmission of HIV in accordance with national guidelines

- In addition urine home pregnancy tests for WOCBP should be performed by the patient every 4 weeks. The results should be communicated via a telephone call visit and recorded in the patient records and in the eCRF.

All subjects should return unused DTG+RPV tablets at next clinic visits for drug accountability purposes. The investigator or designee is responsible for keeping accurate up-to-date accountability documentation for the study drugs (as per pharmacy manual) such as dispensing, returns, and supply.

See Appendix 1 for details of assessment and specific visit requirements.

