2.2 Secondary objectives

- To investigate whether switching patients to DTG/RPV FDC is associated with improvement of lipid profile, patient satisfaction, quality of life and potential for drug-drug interactions, investigated over time through 96 weeks with evaluation (and comparison to control arm) at week 24, 48 and 96.
- To evaluate DTG & RPV trough concentrations
- Changes in cell associated virus (using Peripheral Blood Monoclonal Cell (PBMC) analysis)

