6.10 Early Termination visit

In the case of early termination, every attempt will be made to ensure the subject has a termination visit. At this visit, the following evaluations and procedures are to be performed:

- Symptoms review and adverse events
- Alcohol intake, smoking habit and recreational drug use
- Total cholesterol and lipids (HDL, LDL and triglycerides) (fasted)

CONFIDENTIAL

- PBMC (Required unless exemption documented in site contract i.e. if site does not have capacity to process).
- Blood sampling for measurement of DTG & RPV (PK assessment). (Pre- or post-dose (as appropriate) at early termination visit and/or in the event of virological failure (see section 6.18). A post dose sample will be taken within 20-28 hours.
- Vital signs (pulse, blood pressure: after 10 minutes resting)
- Physical examination (symptom-directed)
- Weight
- Review of concomitant medications
- Laboratory evaluations: haematology and biochemistry (fasting) (Appendix 1)
- HIV RNA viral load
 - Note: In event of viral load failure follow section 6.18 viral failure & resistance assessment procedures.
- CD4 & CD8 count / %
- EuroQoL questionnaire
- Pittsburgh sleep questionnaire
- Patient treatment satisfaction questionnaire
- DDI assessment
- Adherence assessment (including date/time of last dose on PK days including ETV visit and/or in the event of virological failure)
- Pregnancy test for WOCBP (β -HCG).

Patients will be requested to attend for remaining visits and complete study assessments to week 96 even if they are no longer taking study medication.

See Appendix 1 for details of assessments.

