7.5 Dosage schedules

Experimental arm (Baseline visit switch group): One combined Dolutegravir 50mg /Rilpivirine 25mg tablet taken orally once daily (at the same time) for up to 96 weeks with a meal. NB: A high protein drink is not suitable substitute for a meal.

Control arm (deferred week 48 switch group): patients will continue their current boosted PI regimen (or other antiretroviral combination regimen) for 48 weeks. Patients will then be switched to one combined Dolutegravir 50mg /Rilpivirine 25mg tablet taken orally once daily for up to 48 weeks with a meal.

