Both treatment arms to complete all visits.	SCREENING	BASELINE (within 28 days of screening)	WEEK 4 (+/- 7 days)	WEEK 12 (+/- 7 days)	WEEK 24 (+/- 7 days)	WEEK 48 (+/- 7 days)	WEEK 52 (+/- 7 days)	WEEK 60 ¹ (+/- 7 Days)	WEEK 72 (+/- 7 days)	WEEK 96 (+/- 7 days)	30 Day FU (+/- 7 days) (by phone)	Early termination visit

 • HsCRP (optional if agreed with sponsor in writing) • Total protein • Sodium • ALT • Albumin • Creatinine clearance (Calculations: Cockcroft-Gault (requires weight), MDRD, CK-Epi) (* including urinary chemistry)												
Fasting Lipids (Fasted for at least 10 hours except at screening) Including: 
 • Total cholesterol • HDL cholesterol • LDL cholesterol • Triglycerides 	X	X	X	X	X	X	X	X	X	X		X
HIV RNA viral load (In event of viral load failure follow section 6.18 for viral failure, resistance assessment & pharmacokinetic assessment procedures)	X	X	X	X	X	X	X	X	X	X		X
Pre-dose Pharmacokinetic assessment (A post-dose sample will be taken at early termination visit and/or in the event of virological failure (see section 6.18) within 20-28 hours of last dose)			X (Experimental arm only)			X (Experimental arm only)	X (Deferred arm only)			X (Both arms)		X
Blood sampling for PBMC isolation (Required unless exemption documented in site contract i.e. if site does not have capacity to process PBMC samples)		X				X				X		X
Quality of Life Questionnaire		X			X	X				X		X

CONFIDENTIAL

	SCREENING	BASELINE (within 28 days of screening)	WEEK 4 (+/- 7 days)	WEEK 12 (+/- 7 days)	WEEK 24 (+/- 7 days)	WEEK 48 (+/- 7 days)	WEEK 52 (+/- 7 days)	WEEK 60 ¹ (+/- 7 Days)	WEEK 72 (+/- 7 days)	WEEK 96 (+/- 7 days)	30 Day FU (+/- 7 days) (by phone)	Early termination visit
Both treatment arms to complete all visits.												
Patient Treatment Satisfaction Questionnaire		X			X	X				X		X
Pittsburgh Sleep Questionnaire		X			X	X				X		X
DDI Assessment		X			X	X				X		X
Adherence Assessment (Self report at visit) (including date and time of last dose on PK days. Including ETV visit and/or in the event of virological failure)		X	X	X	X	X	X	X	X	X		X
AE Assessment		X	X	X	X	X	X	X	X	X	X	X
Con Med Check	X	X	X	X	X	X	X	X	X	X		X
Drug Dispensing (As per pharmacy manual)		X (Experimental arm only)	X (Experimen tal arm only)	X (Experimen tal arm only)	X (Experimen tal arm only)	X	X	X	X			

CONFIDENTIAL

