10. Pharmacokinetics

[figure not shown]
(j) Pharmacokinetic assessment

Pre-dose plasma concentrations of DTG and RPV at week 4 (experimental arm only), 48 (experimental arm only) and 96. Plus pre/post-dose (as appropriate) at early termination visit and /or in the event of virological failure a post dose sample will be taken within 20-28 hours.

At each time point, the AUC of DTG and RPV post administration will be summarized by the median, Q1, Q3, min, max and number of non-missing values. For each drug, we will compare the evolution of AUC over time using Wilcoxon paired test.

We will use the trapezoidal approach to calculate the area under the curve (AUC). For example, given data t_0, t_1, \dots, t_N and y_0, y_1, \dots, y_N , the area under the curve can be approximated as follows:

$$\int_a^b f(x) dx \approx \frac{1}{2} \sum_{i=1}^N (t_i - t_{i-1})(y_i + y_{i-1})$$
 where t_i is the time value and y_i is the concentration of the antiretroviral drug.

(k) Number of potential DDIs avoided assessment

The number of potential DDIs avoided will be calculated by the difference between the number of interaction drugs graded “amber or red” before and after switching to dolutegravir and rilpivirine. More details are shown in section 3.2.2. The number of DDI avoided will be compared between the two-treatment groups using Mann-Whitney Wilcoxon test. Data will be summarized by the median, Q1, Q3, min, max and number of non-missing values.

11. Other analyses

(l) Changes in quality of life from baseline to week 24, 48 and 96.

The EQ-5D-3L quality of life questionnaires will be analysed using multiple imputation approach to replace missing values (assumption: Missing At Random). Multiple imputation using Chained Equations approach (MICE) will be used to fill in missing data. Therefore, we will create 10 datasets, in which missing data will be imputed from each patient’s other covariables, including all items in the questionnaires, to obtain valid inference and reduce sampling variability resulting from the imputation process. The analysis will include all participants from the mITT population that will complete at least one of the 4 questionnaires (baseline, weeks, 24, 48, and 96). Participants with more than 20% missing data in a specific questionnaire will be excluded from the analysis of the questionnaire.

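### Scheduled PK samples are defined only as pre-dose, with no time-since-dose window, although the objective is trough concentration and last-dose time is recorded

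*Protocol*

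**What the plan says.** **Objective.** Protocol 2.2 states it as "To evaluate DTG & RPV trough concentrations"; SAP 3.1 has the same objective.

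**Scheduled samples.** Protocol 6.8 specifies "Pre-dose blood sampling for measurement of DTG & RPV (PK assessment"), at weeks 4 and 48 in the experimental arm, week 52 in the deferred arm and week 96 in both arms. SAP 10(j) specifies "Pre-dose plasma concentrations of DTG and RPV at week 4 (experimental arm only), 48 (experimental arm only) and 96" and does not name week 52. Neither gives an hours-since-dose limit.

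**Early termination and virological failure.** Protocol 6.8 and 6.10 allow a pre-dose or a post-dose sample, as appropriate. For the post-dose option, 6.10 adds "A post dose sample will be taken within 20-28 hours", and Appendix 1 makes the reference point explicit: "within 20-28 hours of last dose". The pre-dose option there has no window.

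**Dosing and visits.** In Protocol 7.5 the tablet is "taken orally once daily (at the same time) for up to 96 weeks with a meal". The time is to be constant within a person, but morning or evening is left open. Appendix 1 requires a fast of at least 10 hours for chemistry and lipids after screening.

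**Recorded times.** The adherence assessment in Protocol 6.8 and Appendix 1, and in the SAP schedule, captures the date and time of the last dose on PK days.

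**Analysis.** SAP 10(j) summarises an AUC at each time point by median, quartiles and range, and compares time points with a paired Wilcoxon test. It has no rule to exclude, group or adjust samples by time since dose.

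**The concern.** A trough is the concentration at the end of the dosing interval, about 24 h after the last tablet here. Pre-dose means only that the next tablet has not yet been taken. The two coincide for someone who doses in the morning and delays the tablet until after the visit. They do not coincide for someone who takes the tablet with the evening meal and attends a fasting visit the next morning, or for someone who missed the previous tablet.

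Followed as written, the rule therefore admits mid-interval and missed-dose samples to the trough evaluation. A change in a participant's dosing or visit time between weeks 4, 48 and 96 could also appear in a paired comparison as a change in exposure. What is at stake is the interpretation of one secondary objective. The primary endpoint and the interim rule are not affected.

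**Working it through.** The plan gives no figure to reproduce, so the check has two parts.

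**1. Which samples satisfy the rule?**

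The inputs are once-daily dosing with a meal at no set clock time (Protocol 7.5), a fast of at least 10 h (Appendix 1), and the pre-dose requirement (Protocol 6.8). The clock times below are assumptions.

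- Evening doser, meal between 18:00 and 22:00, visit between 08:00 and 10:00. Shortest gap: 22:00 to 08:00 = 10 h. Longest gap: 18:00 to 10:00 = 16 h. All are pre-dose, and all fall outside 20-28 h.
- The same person after one missed tablet: 10 + 24 = 34 h to 16 + 24 = 40 h. Still pre-dose, and still outside 20-28 h.
- Morning doser, last tablet at 08:00 the day before: 24 to 26 h. Pre-dose and inside 20-28 h.

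Fasting combined with dosing at a meal gives an implied floor of about 10 h. It does not bring the sample near 24 h.

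**2. How far from a 24 h value could such samples lie? (illustration only)**

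Half-life is not in the documents. Assume mono-exponential decline with half-life T between 10 and 60 h. The ratio of a sample at h hours to the 24 h value is

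C(h)/C(24) = 2^((24 − h)/T).

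For example, h = 12 and T = 10 gives 2^(12/10) = 2.30; h = 12 and T = 60 gives 2^(12/60) = 1.15.

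| Time since dose | T = 10 h | 14 h | 20 h | 40 h | 60 h |
|---|---|---|---|---|---|
| 10 h | 2.64 | 2.00 | 1.62 | 1.27 | 1.18 |
| 12 h | 2.30 | 1.81 | 1.52 | 1.23 | 1.15 |
| 16 h | 1.74 | 1.49 | 1.32 | 1.15 | 1.10 |
| 20 h | 1.32 | 1.22 | 1.15 | 1.07 | 1.05 |
| 28 h | 0.76 | 0.82 | 0.87 | 0.93 | 0.95 |
| 36 h (12 + 24, one missed tablet) | 0.44 | 0.55 | 0.66 | 0.81 | 0.87 |

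The 20 h and 28 h rows show that the protocol's own window holds a sample within 0.76 to 1.32 times the 24 h value at worst. The 12 h row runs from 1.15 to 2.30. Early samples push values up and missed-dose samples push them down, so the net direction cannot be fixed from the documents.

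**The case against.** **The SAP plans no trough summary.** This is correct: section 10(j) plans AUC medians and a paired test on AUC, and its trapezoidal formula includes a time term. But only one pre-dose sample per scheduled visit is collected, and the trapezoidal rule needs at least two time points. That is a separate problem. Once it is corrected, the single pre-dose values are what remains for the trough objective, and they have no timing rule.

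**The data to repair this are already collected.** This also stands. It makes the gap cheap to close but does not close it, because no analysis rule uses the recorded times.

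**Consistent dosing times protect the paired comparison.** They do in part, but visit clock time is not fixed and missed doses still occur.

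**The Laboratory Manual may set sampling times.** Protocol 6.18 places collection instructions there and it was not supplied, so the point can be made only of the protocol and SAP. An analysis rule would be needed in the SAP even if the manual sets a window.

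Three stronger readings are tempting, and the documents do not support them:

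- A reader might infer that all failure samples are held to 20-28 h while scheduled ones are not. The window covers only the post-dose sample at early termination or failure; a pre-dose sample there is as untimed as a scheduled one.
- A reader might infer that failures would look under-exposed beside scheduled values. Drug concentration at failure is one column in the listing of participants with resistance mutations (SAP 8.2.1(b)), and no comparison with scheduled samples is planned.
- A reader might put a percentage on the inflation of a mean trough. The SAP reports medians and quartiles, and such a figure would need both a half-life and a share of evening dosers, neither of which is in the documents.

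**Conclusion.** The concern holds in a limited form. The protocol and SAP state a trough objective but admit any pre-dose sample to it, and they leave the recorded last-dose time unused. Samples roughly 10-16 h after an evening dose, or well over 24 h after a missed dose, therefore qualify.

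For an individual sample the distortion could be modest or more than twofold, depending on the assumed half-life. Its effect on the planned medians cannot be sized, because the share of out-of-window samples is unknown. The issue is confined to a secondary PK objective in a study that describes itself as a pilot. It is worth correcting because the protocol already contains a suitable window and the data to apply it.

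**What to change.** In SAP 10(j):

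- Define the trough set as samples taken 20-28 h after the recorded last dose, for every scheduled PK visit, including the week 52 deferred-arm sample in Protocol 6.8.
- Base the trough summaries and the paired within-person comparisons on that set.
- List samples outside the window, or with no recorded last-dose time, with their time since dose where known.

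In the SAP 8.2.1(b) resistance listing, show time since last dose beside the drug concentration at failure, whether that sample was pre-dose or post-dose.

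Aligning Protocol 6.8 and Appendix 1 to the same window for scheduled visits is optional, where appointment times allow. It concerns sample timing only and leaves dosing unchanged. Check the Laboratory Manual first so that the documents agree.

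The cost is mainly SAP wording, since last-dose times are already collected. The downside is that some samples leave the trough summary, and fewer participants will have complete pairs.
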